**For bleeds the following should be recorded in patient's diary and pCRF:**

- Date and time of onset of bleeding episode
- Treatment of bleeding episode
- Location of the bleed (specify location e.g. joint, muscular etc.)
- Type of bleed (spontaneous, traumatic)
- Haemostatic drug used for treatment
- Dose level(s), strength(s) and time(s) of administration
- Other therapy used (compression, ice or other)
- Date and time of stop of bleeding episode
- Severity of the bleed (Mild/Moderate or Severe)
- Clinical evaluation of the haemostatic response (Excellent, Good, Moderate or None)

A need for haemostatic rescue therapy with another FVIII product will be assessed by the Physician via phone or during a site visit. Patients treated with FVIII products other than study product during the time of their participation in this study must be withdrawn from the study, see section [9.2.4](#).

**9.3.2.2 Definition of severity of bleeding episodes**

**Mild/Moderate:** Bleeding episodes that are uncomplicated joint bleeds, muscular bleeds without compartment syndrome, mucosal- or subcutaneous bleeds. The details of mild/moderate bleedings should be recorded by the patient in the diary.

**Severe:** All intracranial, retroperitoneal and iliopsoas bleeds must be categorised as severe. Muscle bleeds with compartment syndrome and bleeds associated with a significant decrease in the haemoglobin level (>3g/dl) should also be reported as severe. The details of severe bleeding episodes should be entered in the diary or if the patient is unable to fill in the diary or hospitalised, the Physician or study personnel should enter the data in the patient's medical record and subsequently in the pCRF. Bleeds at other locations than described above can always be considered severe at the Physician's discretion.

**9.3.2.3 Definition of haemostatic response:**

**Excellent:** abrupt pain relief and/or unequivocal improvement in objective signs of bleeding within approximately 8 hours after a single infusion.

**Good:** definite pain relief and/or improvement in signs of bleeding within approximately 8 hours after one infusion, but possibly requiring more than one infusion for complete resolution.

**Moderate:** probable or slight beneficial effect within approximately 8 hours after the first infusion; usually requiring more than one infusion.

**None:** no improvement, or worsening of symptoms within approximately 8 hours after the first infusion; usually requiring more than one infusion.

#### **9.3.2.4 Definition of response during surgery**

Clinical evaluation of haemostatic response during surgery will be evaluated as follows:

- Excellent: blood loss less than expected
- Good: blood loss as expected
- Moderate: blood loss more than expected
- None: uncontrolled bleeding

#### **9.3.2.5 Type of bleed**

- Spontaneous
- Traumatic

### **9.3.3 Assessments for safety**

#### **9.3.3.1 Adverse reactions**

All adverse reactions (ARs), either observed by the Physician or reported by the patient must be recorded and evaluated by the Physician. At each study related contact with the site, the patient should be asked about adverse reactions since the last contact. Please refer to section [11](#) for AR definitions, collection, recording, and reporting.

AR monitoring will be performed from a patient's first exposure to turoctocog alfa until a patient's last visit in the study.

#### **9.3.3.2 Physical examination**

The examination may include:

- Head, ears, eyes, nose, throat and neck
- Respiratory system
- Cardiovascular system
- Gastrointestinal system including mouth
- Genito-urinary system
- Musculo-skeletal system
- Central and peripheral nervous system
- Skin

### **9.3.3.3 Vital signs**

- Pulse
- Blood pressure

Blood pressure and pulse rate will be measured according to local practice; preferably after the patient has rested comfortably for 3 min.

### **9.3.3.4 Laboratory tests**

Results of the following laboratory blood analyses will be recorded if available or performed during the duration of the study:

- FVIII inhibitor
- FVIII recovery
- FVIII trough level
- HIV status, only at visit 1 (includes HIV antibody and viral load, if HIV antibody positive)
- T-cells sub-set: CD4+, only at visit 1 for HIV positive patients

Any blood sampling ordered by the Physician during this study will be the ones regarded as appropriate to provide the best care for the patient at his/her discretion.

Local laboratory results should be reported in the pCRF. It is preferred that the FVIII trough level and the T cells subset: CD4+ values are reported in the listed units, see section [9.3.3.7](#) and [9.3.3.8](#), respectively. However, in the pCRF it will be possible to enter values in other units accepted by Novo Nordisk.

### **9.3.3.5 FVIII inhibitor testing**

Blood sampling for inhibitor detection can be performed according to local clinical practice. As described in the EMA guideline, the Physician is encouraged to test for FVIII inhibitors according to [Table 9-2](#), preferably at least 48 hours after last treatment. If the patient is already being treated with turoctocog alfa at inclusion, the result of the inhibitor sample taken prior to initiated treatment

with turoctocog alfa must be available and negative. After inclusion in the study Novo Nordisk offer to provide analysis for FVIII inhibitors at a Central Laboratory selected by Novo Nordisk.

A positive inhibitor test is defined as  $\geq 0.6$  BU for central laboratory analyses, or above the specific local laboratory reference range. A patient has a confirmed inhibitor if the patient has been tested positive for inhibitors at two consecutive tests preferably within two weeks.

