### 8.2 Endpoint(s)

#### 8.2.1 Primary endpoint

- Incidence rate of FVIII inhibitors ( $\geq 0.6$  BU for central laboratory analyses, or above the specific local laboratory reference range) represented as the percentage of patients developing inhibitors.

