### **9.2.2 Inclusion criteria**

For an eligible patient, all inclusion criteria must be answered “yes”.

1. Informed consent obtained before any study-related activities. (Study-related activities are any procedure related to recording of data according to the protocol).
2. Previously FVIII treated (>150 EDs at the time of first dosing with turoctocog alfa) male patients with the diagnosis of congenital severe and moderately severe haemophilia A (FVIII  $\leq 2\%$ ).
3. The decision to initiate treatment with commercially available turoctocog alfa has been made by the patient/parent and the patient’s treating physician before and independently from the decision to include the patient in this study.
4. Availability of a detailed and reliable patient documentation (patient records, diary, logbook etc.) covering either the last 50 EDs or the last 2 years per patient to confirm treatment modality (i.e. prophylaxis, on-demand or recent surgery) prior to enrolment.
5. A negative FVIII inhibitor test obtained not more than four weeks prior to first dosing with turoctocog alfa.
6. Patients with a history of FVIII inhibitors and who have been immune-tolerized to FVIII through Immune Tolerance Induction treatment must have FVIII plasma recovery level  $\geq 66\%$  of expected level and a FVIII half- life ( $T_{1/2}$ ) of  $\geq 6$  h after a 72 h wash-out period (as demonstrated by available medical records).
7. No clinical suspicion of HIV-1 or, if HIV-1 seropositive, viral load  $< 400.000$  copies/mL and immunocompetent with CD4+ lymphocyte count  $\geq 200/\mu\text{L}$ , as assessed during the last 6 months prior to the Baseline visit.

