### **9.3.3.9 Central Laboratory tests**

If the Physician is performing blood sampling for FVIII inhibitor and/or FVIII recovery test according to local clinical practice, the Physician is encouraged to send these samples to the Central Laboratory for analysis. Central Laboratory data will be reported to Novo Nordisk electronically in a manner that anonymity of patients will be maintained and, to the Physicians by fax or e-mail. Upon review of the laboratory results the Physician should sign and date the laboratory reports. The Central Laboratory is requested only to report analyses dictated by this protocol.

The quality control of the Central Laboratory test results will be performed according to the regulations and specifications set by the authorities at the location of the Central Laboratory used for this study.

Laboratory kits for blood sampling of analyses to be performed by the Central Laboratory will be provided to the sites.

Blood samples analysed by the Central Laboratory for measurement of inhibitors towards FVIII will be performed according to the Nijmegen modification of the Bethesda assay.

Blood samples for FVIII recovery will be analysed by the following two different assays:

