### **9.7.3 Primary endpoint**

The incidence rate of inhibitors ( $\geq 0.6$  BU for central laboratory analyses, or above the specific local laboratory reference range) represented as the percentage of patients developing inhibitors will be calculated and a 1-sided 97.5% upper confidence limit will be provided based on an exact calculation for a binomial distribution. For the calculation of the incidence rate the numerator will include all patients with inhibitors confirmed by laboratory except those patients who have received a positive inhibitor test result after inclusion in the study for a test performed prior to first dose of turoctocog alfa. The denominator will include all patients in the trial exposed to turoctocog alfa,

except those patients who have received a positive inhibitor test result after inclusion in the study for a test performed prior to first dose of turoctocog alfa, these patients will be listed separately.

In addition, the time to inhibitor development will be presented by Kaplan Meier plot. Furthermore, an annualised rate of inhibitors per patient year will be calculated using a Poisson model allowing for over-dispersion with a log-link function and the logarithm of the time spent in the trial as offset, if appropriate.

Analyses and presentations will be made for each treatment regimen (preventive treatment or on-demand treatment) and for all patients, and furthermore for each patient subgroup (Severity of Haemophilia A: severe, moderately severe or patients with surgery/invasive procedure).

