### 10.1 Informed consent form for study patients

Informed consent from all study participants is required before any data is entered into the pCRF and/or any blood samples are sent to the Central Laboratory for analysis.

A voluntary, signed and personally dated informed consent form must be obtained from the patient and/or the patient's parent(s) or LAR prior to any study related activity.

In obtaining and documenting informed consent, the Physician must comply with the applicable regulatory requirement(s) and adhere to the requirements in the Declaration of Helsinki.

If a patient is under age, then the patient's assent must also be obtained according to local requirements.

The task of seeking informed consent can only be performed by the Physician or another medically qualified person delegated by the Physician, if permitted by local regulation, who must sign and date the patient information/informed consent form. If information becomes available that may be relevant to the patient's willingness to continue participating in the study, the Physician must inform the patient/parents and/or the patient's LAR in a timely manner and a revised written informed consent must be obtained.

Prior to any study-related activity, the Physician must give the patient and/or the patient's LAR oral and written information about the study in a form that the patient or the patient's LAR can read and understand. This includes the use of impartial witness where required. In this study the notion of legal representative should be understood as either parents, or LAR, as defined in Member States' national laws, who consents on behalf of the child.

Children, incapable of giving consent, are included as patients in this study in accordance with Health Authority guidelines for development of FVIII products.

**Consent:** As a child is unable to provide legally binding consent, informed consent must be obtained from the parents/LAR on the child's behalf. The specific and written informed consent of the parents/LAR must be sought prior to enrolling a child in the study. Information should be given by an experienced Physician to each parent, or the LAR, on the purpose of the study and its nature.

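### An inhibitor test is positive or negative by the rule of whichever laboratory ran it, with no comparison to baseline, so an unchanged low titre can count as a new inhibitor in some patients

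*Protocol*

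**What the plan says.** **Entry.** Protocol section 9.2.2, criterion 5, requires "A negative FVIII inhibitor test obtained not more than four weeks prior to first dosing with turoctocog alfa". It names no cut-off, assay or laboratory. Section 9.1.1 admits patients who have already started turoctocog alfa. For them, section 9.3.3.5 says that the result from before the start of treatment "with turoctocog alfa must be available and negative".

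**Access to central testing.** Section 9.3.3.5: "After inclusion in the study Novo Nordisk offer to provide analysis for FVIII inhibitors at a Central Laboratory selected by Novo Nordisk". Section 10.1 requires consent before "any blood samples are sent to the Central Laboratory for analysis". Under section 9.3.3.9 central testing during the study is optional: "the Physician is encouraged to send these samples to the Central Laboratory for analysis". The central assay is the Nijmegen modification of the Bethesda method; no local assay is specified.

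**Positive and confirmed.** Section 9.3.3.5 sets the threshold at 0.6 BU "for central laboratory analyses, or above the specific local laboratory reference range". The primary endpoint in section 8.2.1 carries the same alternative, "or above the specific local laboratory reference range". Two consecutive positive tests confirm an inhibitor.

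**Analysis.** The section 9.7.3 numerator takes every laboratory-confirmed inhibitor "except those patients who have received a positive inhibitor test result after inclusion in the study for a test performed prior to first dose". All exposed patients, with the same exception, form the denominator.

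**The concern.** The primary endpoint is meant to show inhibitors that arise on turoctocog alfa. That requires a negative at entry and a positive at follow-up to mean the same thing. Here they need not. The entry test can be read against a local range and the follow-up test against 0.6 BU by a specified central assay. If the two thresholds differ, a change of laboratory alone can produce an event with no change in the patient.

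A pre-existing low titre is not far-fetched in this population. Criterion 6 in section 9.2.2 admits patients with past inhibitors after immune tolerance induction and sets recovery and half-life limits for them, but no titre limit.

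Very few true events are expected, so a single artefact would make up most or all of the observed rate.

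**Working it through.** The protocol states no figure for this point, so there is none to reproduce. The check has three parts.

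**1. Which patients are exposed to a change of laboratory**

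| Patient | Pre-first-dose result | Follow-up result | Does the section 9.7.3 exception protect? |
|---|---|---|---|
| Not yet dosed at Visit 1, 0 exposure day sample sent centrally | Local (criterion 5) plus central | Local or central | Yes: a central positive before first dose removes the patient |
| Not yet dosed at Visit 1, no central 0 exposure day sample | Local only | Local or central | No |
| Already on turoctocog alfa at inclusion | Local only, because central testing needs inclusion and consent | Local or central | No: no pre-dose sample can still be drawn |
| Tested at one local laboratory throughout | Local | Local | Not needed: one rule applies throughout |

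For a patient already treated, a Visit 1 sample is labelled 0 exposure days because the count starts at baseline, but it is taken after first exposure and cannot serve as a pre-dose test.

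**2. When an unchanged titre becomes an event**

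Let t be a stable true titre and L the local upper limit. With error-free assays, local negative then two central positives requires 0.6 ≤ t ≤ L.

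- L = 0.6 BU or lower: essentially no window.
- L = 0.8 BU: window 0.6 to 0.8 BU.
- L = 1.0 BU: window 0.6 to 1.0 BU.

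These values of L are assumptions. Requiring two positives does not help, because a stable titre passes both tests.

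With measurement error (assumed: normal, independent, coefficient of variation 20%) and t = 0.7 BU, the standard deviation is 0.2 × 0.7 = 0.14 BU. The chance of one central positive is Φ((0.7 − 0.6)/0.14) = 0.762, and of two 0.762² = 0.581. Multiplying by the chance of a local negative at entry:

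- L = 0.6: 0.238 × 0.581 = 0.14
- L = 0.8: 0.762 × 0.581 = 0.44
- L = 1.0: 0.984 × 0.581 = 0.57

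These are probabilities for a patient who has such a titre and changes laboratory. The documents do not say how many such patients there are.

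**3. Effect on the primary result**

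Inputs: about 70 patients included and about 50 completing (section 9.2.1); one-sided 97.5% exact binomial upper limit (section 9.7.3). The denominator is all exposed patients, so 70 is the relevant planned number.

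For 0 events the limit is 1 − 0.025^(1/n). For 1 event it is the p that solves (1 − p)^n + np(1 − p)^(n−1) = 0.025.

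| n | 0 events | 1 event |
|---|---|---|
| 70 | 0%, upper limit 5.13% | 1.43%, upper limit 7.70% |
| 50 (completers, for comparison) | 0%, upper limit 7.11% | 2.00%, upper limit 10.65% |

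True events expected at the protocol's background rate of 3 per 1000 patient-years (section 7.2):

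- 70 patients for one year each (assumed): 70 × 0.003 = 0.21.
- 70 patients for 100 exposure days at three per week (assumed): 100/3/52.18 = 0.639 years each, 44.7 patient-years, 44.7 × 0.003 = 0.13.

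One artefact would therefore exceed the expected number of true events several times over.

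**The case against.** A reader might infer that baseline is always judged locally and follow-up always by the central 0.6 BU cut-off. The protocol does not say that. The alternative central-or-local rule applies at follow-up too, central testing is only encouraged, and a positive from a local laboratory alone also counts (section 11.2). A patient tested at one local laboratory throughout meets one rule.

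Patients not yet dosed are partly covered. Table 9–2 recommends a sample at 0 exposure days, kits are supplied, and a central pre-dose positive removes the patient from numerator and denominator. That stands, and it limits the gap to patients already treated and those with no central 0 exposure day sample.

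A reader might also infer that one misclassified case decides the study. It does not: section 9.7.1 rules out formal hypothesis testing, and no threshold is set. A confirmed inhibitor is also a serious adverse reaction and would be listed individually. But the listing can expose an artefact only if titre, assay and local limit are known. Section 9.3.3.4 asks for local results and section 9.3.4.7 for past inhibitor results if available; neither calls for the assay or the local limit. The pCRF itself is not shown, so it may already hold some of this.

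Two further points stand. Local testing follows from the non-interventional design, and section 9.9 admits that routine assessments may affect interpretation. In an immunogenicity study a rule that errs toward counting is defensible, which is why the primary definition should stay. A supplementary analysis might normally be left to the SAP, but the numerator is fixed in section 9.7.3, and no SAP can use data that were never recorded.

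**Conclusion.** The point holds in limited form. For patients already on turoctocog alfa at inclusion, or without a central 0 exposure day sample, the protocol allows a local negative at entry and central positives at follow-up, and counts the result as a new inhibitor with no requirement that anything changed. With about 70 exposed patients, one such case moves the observed rate from 0% to 1.43% and the upper limit from 5.13% to 7.70%.

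This rests on a local limit above 0.6 BU, or on assay differences or noise with a similar effect; on a patient with a stable titre in that band; and on a move from local to central testing. The protocol gives no local limits and no prevalence of such titres, so how often this would happen cannot be estimated. If all local limits were 0.6 BU or lower, the route would largely close apart from assay differences and noise, but nothing in the protocol ensures that.

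**What to change.** Keep the primary definition and add the following.

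1. **Data.** Record numeric titre, assay type and local upper limit for the criterion 5 test and for every local follow-up test, where the laboratory reports them.
2. **Analysis (section 9.7.3).** Add a supplementary analysis applying 0.6 BU or more to all numeric titres, at baseline and follow-up. A confirmed inhibitor is incident if the pre-first-dose titre was below 0.6 BU, or if the titre clearly rose from a baseline of 0.6 BU or more. Fix the rise criterion in advance. Without the second condition, a patient who starts just above 0.6 BU and later develops a high titre would be dropped.
3. **Listing.** List separately any confirmed case whose baseline is known only as within a local range with an upper limit above 0.6 BU.
4. **Samples.** For patients not yet dosed at Visit 1, ask that any 0 exposure day sample drawn goes to the central laboratory.

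The cost is minor changes to a paper CRF in a running study, one extra analysis and one listing, with no added visits or blood draws. Two limits remain: laboratories that report only positive or negative stay on the local rule, and a common cut-off does not remove differences between assays. Item 4 cannot help patients already treated at inclusion; for them items 1 to 3 are what is available.

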**Table 9–2 Recommended laboratory scheme for FVIII inhibitors and recovery**

	0 EDs	10-15 EDs	50-75 EDs	~100 EDs
FVIII inhibitors	X 	X 	X 	X 
FVIII recovery	X	X	X	X

A 48 hours washout period is recommended

[figure not shown]
In the event that a patient has a positive inhibitor test obtained within 4 weeks prior to first dose of turoctocog alfa, the patient cannot be included in the study according to inclusion criteria no. 5, see section [9.2.2](#). In the event that a patient has a positive inhibitor test result after inclusion in the study for a test performed prior to first dose of turoctocog alfa, the patient may proceed in the study but will not be included in the full analysis set. In the event that a patient has a positive inhibitor test ( $\geq 0.6$  BU for central laboratory analyses, or above the specific local laboratory reference range) after inclusion and dosing in the study, the patient should visit the clinic again according to local practice (recommended to be performed as soon as possible - preferably within 2 weeks) to take a confirmatory inhibitor test on a separately drawn sample. The confirmatory sample should preferably be taken prior to any change of treatment. Even if the second inhibitor test is positive, the patient may continue in this study.

If this is decided, dosing, dosing frequency and more frequent visits for inhibitor sampling, if applicable, will be decided by the Physician based on the clinical evaluation. If a patient is to be withdrawn due to a confirmed inhibitor test, the Physician is encouraged to schedule an End of study visit (Visit 3) according to local clinical practice, and preferably within 1 month.

A positive inhibitor test should be reported as an AESI, see section [11.3](#). If the presence of inhibitors is confirmed by a second test this should be reported as a serious adverse reaction (SAR), see section [11.3](#). If the second inhibitor test is negative this should be reported as a follow-up to the reported AESI, see section [11.4](#). When lack of therapeutic effect is indicated by bleeding or laboratory findings, the Physician is encouraged to sample for FVIII inhibitor detection.

It is recommended that the Physician should upon a clinical suspicion of inhibitor development perform a FVIII inhibitor test.

The recommended process of inhibitor testing in case of a positive inhibitor test during the study is outlined in [Figure 9–1](#).

Recommended sampling times: 0 ED, 10-15 ED, 50-75 ED, ~100 ED- or in case of lack of therapeutic effect

